9.4.3 ANALYSIS OF THE SECONDARY EFFICACY ENDPOINT(S)

For each secondary efficacy endpoint:

Similar to the primary endpoints described above, we will examine percent change in all continuous secondary outcomes measures. In addition, we will also calculate raw change from baseline (raw change = (postbaseline value – baseline value). Raw change and percent change in each continuous endpoint will be calculated in a manner analogous with described above for the

primary endpoint. Raw changes in measures from baseline will be assessed using a paired t-test or a Wilcoxon signed-rank test when data are non-normally distributed. Output for each endpoint will include the mean, its 95% confidence interval and the p-value if a t-test is performed. If the endpoint is not normally distributed, median values, and the 25th and 75th percentiles will be presented, along with the p-value from the Wilcoxon signed-rank test.

Similar analyses will be performed to examine interval changes in continuous measures from Baseline to Week 6 (when applicable).

Growth data collected during the study will be summarized descriptively at each time point and converted to age-sex specific z-scores using normative data. Raw changes in BMI and weight as well as Z-scores will be examined using the methods described above.

- Patients with no week 12 measurements will be excluded from the secondary efficacy analyses (observed case data only will be used). In a sensitivity analysis, for subjects with missing week 12 data, we will carry forward their week 6 measurements and re-assess the primary outcomes. Similar analyses will be used to examine the mITT and the PPAS datasets.

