3 ENDPOINTS

Primary Endpoint:

- Percent change in ALT from Baseline to Week 12

Secondary Endpoints:

- Absolute change in ALT from Baseline to Weeks 6 and 12
- Percent change in ALT from Baseline to Week 6 and the mean of Week 6 and Week 12
- Absolute change and percent change in hepatic steatosis from Baseline to Week 12 as measured by MRI (volumetric fat fraction-hepafat)
- Absolute change and percent change in pancreatic fat from Baseline to Week 12 as measured by MRI (HepaFat)
- Absolute change and percent change in AST from Baseline to Week 6 and Week 12
- Absolute change and percent change in insulin sensitivity as assessed by fasting insulin, fasting glucose, and HOMA-IR from Baseline to Week 6 and Week 12
- Absolute change and percent change in GGT from Baseline to Week 6 and Week 12
- Absolute change and percent change in serum lipids including total cholesterol, non-HDL-C, HDL-C, VLDL-C, LDL-C, and triglycerides (TG) from Baseline to Week 6 and Week 12
- Absolute change and percent change in apolipoproteins including apoA-1, apoB, apoC-II, apoE and apoCIII
- Absolute change and percent change in inflammatory markers such as hsCRP, IL-1B, IL-6 and procollagen III.
- Absolute change and percent change in lipoprotein particle sizes (VLDL, HDL, LDL, chylomicrons [NMR])
- Absolute change and percent change in post-prandial lipids (total cholesterol, non-HDL-C, HDL-C, VLDL-C, LDL-C, TG, lipoprotein particle size)
- Absolute change and percent change in rate of de novo lipogenesis using stable isotope tracers
- Change in body composition measures by AMRA from Baseline to Week 12
- Absolute change and percent change in liver inflammation and fibrosis (LIF and cT1) scores by MRI (Liver MultiScan).
- Absolute change and percent change in anthropometric measures including height, weight, body mass index, and waist circumference from Baseline to Week 12

- Safety related endpoints including adverse events (AEs), vital signs, clinical labs, hematology and urinalysis
 - Treatment tolerance and compliance
-

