9.2 SAMPLE SIZE DETERMINATION

The sample size for this study is 36 completed participants. A percent change from baseline of approximately 20% is considered to be clinically meaningful. Assuming a two-sided test at the 5% significance level, 36 completed participants will provide 81% power to detect a percent change from baseline of 20% (effect size = 0.5), if the standard deviation is 40%. Additionally, assuming a drop-out rate of 10%, a total of 40 participants is needed for enrollment into the study to ensure an adequate number of subjects complete the trial. Power was calculated using a two-sided Wilcoxon test with a 0.05 significance level using PASS v. 14.0.8 (Kaysville, UT).

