9.3 POPULATIONS FOR ANALYSES

- Intention-to-Treat (ITT) Analysis Set: all enrolled participants. All efficacy summaries and analyses will be performed using the ITT.
- Modified Intention-to-Treat Analysis (mITT) Set: all enrolled participants who took at least one dose of study intervention and have liver enzymes performed at Baseline and Week 12. Confirmatory efficacy analyses will be performed using the mITT.
- Safety Analysis Set (SAS): all enrolled participants who took at least one dose of study intervention. All safety summaries will be performed using the SAS.
- Per-Protocol Analysis Set (PPAS): the subset of the participants in the full analysis (ITT) set who complied with the protocol sufficiently (e.g., took at least 80% of study intervention for 80% of the days within the 12-week period) and did not have any major protocol deviations. Confirmatory efficacy and safety analyses will be performed using the PPAS.

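### Read literally, Section 9.4.3 drops children with no Week 12 measurement from the Week 6 secondary efficacy endpoints, although their Week 6 values were observed

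*Combined protocol and SAP*

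**What the plan says.** Section 3 lists several secondary endpoints with a Week 6 component:

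- For ALT on the raw scale, the entry is "Absolute change in ALT from Baseline to Weeks 6 and 12".
- For ALT on the relative scale, two further summaries are named, the second of which also needs the later visit: "Percent change in ALT from Baseline to Week 6 and the mean of Week 6 and Week 12".
- For the other transaminase, both scales are used: "Absolute change and percent change in AST from Baseline to Week 6 and Week 12".
- GGT, insulin sensitivity and serum lipids are each to be assessed on both scales at the same two visits.

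Section 9.4.3 sets the method for every secondary efficacy endpoint and brings the earlier visit into its scope: "Similar analyses will be performed to examine interval changes in continuous measures from Baseline to Week 6 (when applicable").

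Its missing-data rule then reads: "Patients with no week 12 measurements will be excluded from the secondary efficacy analyses (observed case data only will be used"). The sensitivity analysis that follows says that, for children missing Week 12, "we will carry forward their week 6 measurements and re-assess the primary outcomes".

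Section 9.3 defines the ITT set as everyone enrolled and says: "All efficacy summaries and analyses will be performed using the ITT". The mITT set requires liver enzymes at both Baseline and Week 12, and Section 9.4.3 repeats its analyses in that set.

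**The concern.** A Week 6 change needs two values, Baseline and Week 6. The stated rule adds a third condition, a Week 12 measurement, that has no bearing on whether the Week 6 change can be calculated. The Week 6 sample is then selected on events after Week 6.

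Those events may be related to response. Section 7.2 allows an investigator to withdraw a child from the study for an adverse event, a laboratory abnormality, disease progression or an interruption of drug of 14 days or more. With one arm and no comparator, any selective loss passes straight into the reported mean change. Section 7.2 also says that children who leave after more than 4 weeks of treatment are not replaced.

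The rule also sits oddly with its neighbours. The carry-forward analysis would use such a child's Week 6 ALT in place of the missing Week 12 value, while the literal rule keeps the same value out of the Week 6 analysis. It also does not fit the assignment of all efficacy analyses to the full enrolled set.

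**Working it through.** **1. Which endpoints are touched.** The rule changes the sample only where an endpoint can be calculated without Week 12.

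| Endpoint | Needs Week 12? | Changed by the rule? |
|---|---|---|
| Week 6 change in ALT, AST, GGT, insulin sensitivity, serum lipids | No | Yes |
| Mean of Week 6 and Week 12 ALT | Yes | No |
| MRI fat, body composition, anthropometry to Week 12 | Yes | No |
| Safety endpoints (Section 9.4.4, safety set) | Not an efficacy analysis | No |
| Primary endpoint (Section 9.4.2) | Yes | No |

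**2. The plan's own figures (Section 9.2).** Inputs: 36 completers, a 20% change, SD 40%, two-sided 5%, Wilcoxon test, 10% drop-out.

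- Standardized effect: 20/40 = 0.5.
- Effective n for the signed-rank test on normal data: 36 × 3/π = 34.4. Noncentral t power is 81.2%; a simulation of 20,000 signed-rank tests gives 81.5%. The stated 81% reproduces.
- Enrolment: 36/(1 - 0.10) = 40. This reproduces.

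**3. How many children.** Planned drop-outs: 40 - 36 = 4. The documents do not say when they leave. If all leave before Week 6, no child is affected. If all leave after Week 6 with a Week 6 value, 4 of 40 (10%) are.

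**4. Precision at Week 6.** Assume SD 40% at Week 6 as well. The 95% half-width is t(0.975, n-1) × 40/√n.

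- n = 36: 13.5 points.
- n = 40: 12.8 points.

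Power at a standardized effect of 0.5 would go from 81.2% to 85.3%. The precision lost is small, and both figures assume the maximum of 4 affected children.

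**5. Shift in the Week 6 mean.** Assume the 36 completers average -20%. Let k excluded children average m at Week 6. The mean of all observed values is (36 × (-20) + k × m)/(36 + k). The rule as written reports -20% in every row.

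| k | m (assumed) | Calculation | All-observed mean |
|---|---|---|---|
| 4 | -40% | (-720 - 160)/40 | -22.0% |
| 4 | -20% | (-720 - 80)/40 | -20.0% |
| 4 | 0% | (-720 + 0)/40 | -18.0% |
| 4 | +20% | (-720 + 80)/40 | -16.0% |
| 4 | +50% | (-720 + 200)/40 | -13.0% |
| 1 | 0% | (-720 + 0)/37 | -19.5% |
| 1 | +50% | (-720 + 50)/37 | -18.1% |

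The shift can be zero or go either way. Seven points needs all four drop-outs to leave after Week 6 and to average +50%.

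**The case against.** The strongest reply is that the authors meant a per-visit analysis. The rule's own parenthesis speaks of observed cases, which usually means using whatever is observed at each visit. The paragraph closely resembles the one for the primary endpoint in Section 9.4.2 and still refers to primary outcomes inside the secondary section, so it looks like reused wording. This may well be right about intent. The words on the page nevertheless exclude patients, no other section gives a Week 6 rule, and two programmers could build different Week 6 samples from this text.

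Four stronger readings are tempting, and the documents do not support them.

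- **Every secondary endpoint is affected.** The rule covers secondary efficacy analyses. Safety endpoints are listed as secondary but analysed under Section 9.4.4.
- **The children lost are those who stop drug.** Section 7.1 separates stopping gemcabene from leaving the study and asks that remaining procedures be completed; Section 10.1.2 says the same for several haemoglobin and renal stops. Such children should have Week 12 values. Only those who leave or miss Week 12 are at issue. The plan does not say whether Early Termination blood results count as Week 12; if they do, fewer children are affected.
- **The Week 6 result is biased toward benefit.** This is plausible, but the documents give neither the timing of drop-out nor the Week 6 values of those who leave.
- **The Week 6 data are thrown away altogether.** For ALT they enter the carry-forward sensitivity analysis. They do not enter the Week 6 endpoint, and the text does not clearly extend carry-forward to AST, GGT, lipids or insulin measures.

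**Conclusion.** The point holds as a defect in a stated rule, on a literal reading of Section 9.4.3. It makes membership of the Week 6 efficacy sample depend on later events and leaves out observed data that those endpoints need.

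The size is modest: 0 to 4 of 40 children at the planned drop-out, and at most about 0.7 points of half-width. The possible shift in the mean is of unknown sign, and is 0 to 7 points toward a smaller reduction if the excluded children average between -20% and +50%. These figures rest on an assumed completer mean of -20%, an assumed SD of 40% at Week 6 and, at the maximum, all four drop-outs leaving after Week 6 with a value recorded. The wording should be corrected before analysis because the correction costs almost nothing and removes a choice that could otherwise be made after seeing the data.

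**What to change.** Replace the exclusion sentence in Section 9.4.3 with: *Each secondary efficacy analysis includes all ITT participants with a Baseline value and a value at every visit the endpoint uses; Week 6 analyses include participants with no Week 12 measurement.* Naming every visit the endpoint uses also settles the mean of Weeks 6 and 12, which needs both.

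Add to Section 9.3 that the Week 12 liver-enzyme requirement of the mITT set does not apply to Week 6 endpoints. Otherwise the same exclusion returns when the analyses are repeated in that set.

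The cost is two sentences of text. No data collection, sample size or primary analysis changes.

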4 STUDY DESIGN

4.1 OVERALL DESIGN

Hypothesis

Gemcabene (300mg a day) for twelve weeks will be safe and will decrease ALT and percent hepatic steatosis by MRI in children with NAFLD.

Type of trial

- Phase 2a open label trial
- Multicenter, prospective, open label trial in 40 children (36 who complete the study) with NAFLD

Treatment group

- Gemcabene 300 mg once a day

Number of clinical centers

- 3 pediatric sites

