7 STUDY INTERVENTION DISCONTINUATION AND PARTICIPANT DISCONTINUATION/WITHDRAWAL

7.1 DISCONTINUATION OF STUDY INTERVENTION

Discontinuation from gemcabene does not mean discontinuation from the study, and remaining study procedures should be completed as indicated by the study protocol. If a clinically significant finding is identified (including, but not limited to changes from baseline) after enrollment, the investigator or qualified designee will determine if any change in participant management is needed. Any new clinically relevant finding will be reported as an adverse event (AE).

The data to be collected at the time of study intervention discontinuation (Early Termination Visit) will include the following:

- Blood tests
- MRI
- Vital signs, physical measurements, and a physical examination
- Questionnaires (Food Frequency Questionnaire, PROMIS Questionnaires, Beverage Questionnaire, Physical Activity Assessment)
- Urine collection and pregnancy test (in WOCBP)
- Adverse event and concomitant medication review

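### The Week 6 carry-forward in section 9.4.3 cannot work for the MRI endpoints, because no MRI is scheduled at Week 6, and section 9 gives the Early Termination MRI and central labs no role

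*Combined protocol and SAP*

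**What the plan says.** Section 4.1 puts liver fat in the study hypothesis beside ALT: gemcabene "will decrease ALT and percent hepatic steatosis by MRI". Section 3 defines the endpoint at a single post-baseline time: "Absolute change and percent change in hepatic steatosis from Baseline to Week 12 as measured by MRI (volumetric fat fraction-hepafat".

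On missing data, section 9.4.3 gives the main rule, "Patients with no week 12 measurements will be excluded from the secondary efficacy analyses (observed case data only will be used", and one sensitivity analysis: "for subjects with missing week 12 data, we will carry forward their week 6 measurements and re-assess the primary outcomes". It then adds: "Similar analyses will be used to examine the mITT and the PPAS datasets". Section 9.3 defines the mITT set as "all enrolled participants who took at least one dose of study intervention and have liver enzymes performed at Baseline and Week 12"; the PPAS depends on compliance and the absence of major deviations.

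On data collection, the MRI row of Table 1 is marked at Baseline, Week 12, Early Termination and Weeks 28, 36 and 60. The Week 6 cell is blank. Section 7.1 introduces the ET assessments with "The data to be collected at the time of study intervention discontinuation (Early Termination Visit) will include the following", and the list includes blood tests and MRI. Table 2 schedules the central liver panel (ALT, AST) at ET.

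**The concern.** A sensitivity analysis for missing data should show how the result moves when participants without the endpoint are brought back in. For the MRI endpoints the stated rule has nothing to bring back. A report that followed it would present a sensitivity analysis identical to the main analysis, and readers could take the agreement as evidence of robustness.

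The sentence also appears to have been carried over from section 9.4.2 unchanged. Because it re-assesses the primary outcomes, AST, GGT and the lipids have no missing-data check on a literal reading either, although they do have Week 6 values.

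Meanwhile the ET visit schedules the measurements that could fill some gaps, and section 9 is silent on them. This reaches ALT too. A child who leaves after Week 6 would be represented by the Week 6 value despite a later ET value. A child who leaves before Week 6 would be absent even from the sensitivity analysis. In a single-arm, open-label study with no concurrent control, selective loss of participants acts directly on the before-after estimate. A rule for ET data chosen after results are known would be hard to defend.

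**Working it through.** **1. The plan's own figures (section 9.2).** Inputs: 36 completers, 20% change, SD 40%, effect size 20/40 = 0.5, two-sided 5% level, 10% drop-out.
- One-sample t-test power at n = 36: 83.1%.
- Wilcoxon, using n × 3/π = 36 × 0.955 = 34.4: 81.2%. A simulated signed-rank test (20,000 runs, normal data) gives 81.5%. The stated 81% is reproduced.
- Enrolment: 36/(1 - 0.10) = 40, as stated.

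These figures are for ALT. The documents give no expected change or SD for steatosis.

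**2. Which values the rule can carry forward.**

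| Endpoint group | Week 6 value scheduled | ET value scheduled | Effect of Week 6 carry-forward |
|---|---|---|---|
| ALT, AST, GGT, fasting lipids | Yes (Table 2) | Yes | Fills those who reached Week 6 |
| Steatosis, pancreatic fat, LIF/cT1, body composition | No (Table 1) | Yes | Changes no record |

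**3. The other analysis sets.** The mITT requires Week 12 liver enzymes and the PPAS requires compliance. Neither supplies a missing scan, so for MRI both are again observed-case analyses.

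**4. Number at stake.** 40 - 36 = 4 participants without Week 12 data at the planned drop-out. Week 6 carry-forward recovers 0 of 4 scans. ET scans could recover 0 to 4, since the documents do not say how many leavers attend that visit.

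**5. Possible shift in the mean (all changes assumed; the -20% is borrowed from the ALT planning figure).** Mean over 40 = (36 × completer mean + 4 × leaver mean)/40.
- Leavers 0%: (36 × -20 + 4 × 0)/40 = -18%, which is 0.90 of the completer mean.
- Leavers +20%: (36 × -20 + 4 × 20)/40 = -16%, which is 0.80 of it.

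**6. Set against sampling error (ALT SD of 40% borrowed for steatosis, an assumption).**
- 95% confidence half-width at n = 36: 2.03 × 40/√36 = 13.5 points, against a shift of 2 to 4 points.
- In the +20% case, with SD 40% within each group: variance = (35 × 1600 + 3 × 1600 + (36 × 4/40) × 40²)/39 = 66,560/39 = 1,707, so SD = 41.3%. Then t = -16/(41.3/√40) = -2.45 and p is about 0.02. The test against zero would still be significant.

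**The case against.** The strongest reply concerns who is actually lost. A reader might infer that children who stop the drug, perhaps for liver findings, vanish from the steatosis result. The documents do not support that. Section 7.1 says that stopping gemcabene is not leaving the study and that remaining procedures should be completed. Section 10.1.2 says the same for hemoglobin and renal stops. Section 9.4.2 analyses participants whether or not they took the drug. A child who only stops treatment should therefore have a Week 12 scan and count as observed. The gap concerns those who leave the study or miss Week 12. This part of the reply stands.

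A reader might also infer that an on-treatment MRI is already in hand for each leaver. It is scheduled, not assured. Participants lost to follow-up (section 7.3) will not have one, and those who withdraw may decline. Section 7.2 allows withdrawal after 14 or more days without drug, so an ET scan may be off treatment. This stands too, and it limits what any ET rule can claim.

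That ET data go unused is read from silence; nothing in section 9 forbids their use. Steatosis is also one of many secondary endpoints in a Phase 2a study powered on ALT only, the assumed shift is small beside the sampling error, and the primary endpoint has a Week 6 check that works for those who reached Week 6. All of this bears on size. None of it makes the stated rule workable for the MRI endpoints.

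**Conclusion.** The point holds in this limited form. For four groups of MRI endpoints, including one named in the hypothesis, the planned missing-data sensitivity analysis is empty. For the remaining secondary endpoints it is missing on a literal reading. The ET measurements have no stated role for any endpoint. That part rests only on comparing Table 1, Table 2 and section 7.1 with section 9, and needs no assumption.

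The size is moderate and mostly unknown. About 4 of 40 participants are affected if drop-out is as planned, and 0 to 4 of them could be recovered. The -18% and -16% figures illustrate the scale under assumed values and do not estimate bias. On those values, with the ALT SD borrowed, the test against zero would not change; what may move is the estimated reduction. The documents do not support a claim that the steatosis result is biased by a known amount. The correction should be made before analysis, because the study is open-label and the rule can still be set without reference to the results.

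**What to change.** Keep observed-case as the main analysis, and make these changes to the text:

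1. In 9.4.3, replace *primary outcomes* with *secondary outcomes* in the sensitivity sentence.
2. In 9.4.2 and 9.4.3, define the sensitivity analysis along these lines: *for participants with no Week 12 value, the last available post-baseline value up to the Week 12 visit is used, including the Early Termination visit; for MRI endpoints this is the Early Termination scan.* The limit keeps the Week 28, 36 and 60 scans from standing in for Week 12.
3. Report time on treatment and days since last dose for every value used this way, and the number of participants still without any value.
4. Reconcile the visit definitions. Section 7.1 places the ET visit at drug discontinuation while also asking for the remaining procedures, and section 8.3.11 times follow-up from Week 12 or ET. The plan should say which visit supplies the Week 12 analysis value when a participant has both.

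The cost is wording only; no visit, scan or sample is added. The downside is that ET values reflect shorter and variable exposure and may be off treatment, so the result can only be a sensitivity analysis. Participants with no ET scan stay missing.

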9.4.4 SAFETY ANALYSES

Each AE will be counted once only for a given participant in each summary table, and will be presented based on severity, frequency, and relationship of AEs to study intervention by System Organ Class (SOC) and preferred term groupings. For each AE, the severity, relationship, expectedness, outcome, and duration will be presented in a table. Adverse events leading to premature discontinuation from the study intervention and serious treatment-emergent AEs will be presented either in a table or a listing. AEs will be tabulated and described using counts and percentages with associated 95% confidence intervals.

